
Statistical Methods:
 
A comprehensive statistical analysis plan will be developed for this study. The efficacy results from Part 1 and Part 2 will not be combined.
 
Part 1
 
At the end of Part 1, an unblinded dose selection committee will review at least the results from the following assessments conducted during Part 1: (1) the AUC of the NRS-R pain intensity scores through 72 hours; (2) total postsurgical opioid consumption; (3) the time to first opioid rescue, and (4) safety data. Based on a clinical evaluation of the data, the committee will determine the apparent efficacy and safety of each of the three liposome bupivacaine dose levels tested and will recommend a dose level to be tested during Part 2 of the study.
 
Descriptive summaries will be provided by treatment group. Each dose of liposome bupivacaine will be compared to placebo using analysis of covariance (ANCOVA) with treatment as the main effect and the baseline NRS-R pain intensity score as a covariate for AUC of the NRS-R pain intensity scores through 72 hours, using analysis of variance (ANOVA) after a natural logarithm transformation for total postsurgical opioid consumption, and using a log-rank test for time to first opioid rescue. Summary statistics will be provided by treatment group for the safety assessments.
 
Adverse events and SAEs will be summarized by treatment group.
 
At the end of the study, descriptive summary statistics, without statistical tests, will be provided by treatment group for the other efficacy endpoints.
 
Part 2
 
The efficacy results from Part 2 will not include data from Part 1. Descriptive summaries will be provided by treatment group. Liposome bupivacaine will be compared to placebo using ANCOVA with treatment as the main effect and the baseline NRS-R pain intensity score as a covariate for AUC of the NRS-R pain intensity scores through 72 hours, using ANOVA after a natural logarithm transformation for total postsurgical opioid consumption, and using a log-rank test for time to first opioid rescue. For analyzing the two secondary endpoints a hierarchical testing procedure will be used. First the total postsurgical opioid consumption will be tested. If the test is significant at the 0.05 level then, and only then, time to first opioid rescue will be tested. This result will be declared statistically significant at the 0.05 significance level.
 
Safety data from Part 1 and Part 2 will be combined and summarized by treatment group.
		

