7.1.3. Handling Missing Values

Surgery Date or Time

It is expected that all necessary information on surgery (start and stop date and time) and postsurgery rescue medication (start dates and times, doses, frequency) will be complete. Any such information that is missing and cannot be obtained through query resolution may be imputed, on a case-by-case basis, in a conservative manner that minimizes bias. For example, if pain medication taken on Day 1 has no time of administration recorded, the imputed time will be the end of surgery.

PCA Pump Interval Data

For some subjects, individual doses from the PCA pump were not collected. For some subjects the individual doses were not collected for the whole 72 hours and for some it was not collected for parts of the 72 hours. For these data the intervals during which medication was delivered via the PCA pump are known. So what was entered in the database was the medication, the start date and time of the interval, the stop date and time of the interval, and the total dose received.

For these cases, for purposes of imputing pain scores using the wWOCF imputation, it will be assumed that a dose was given at the beginning of the interval, a dose was given at the end of the interval, and a dose was given in the middle of the interval.

For these cases, for purposes of calculating the total postsurgical opioid consumption through the various time intervals, it will be assumed that the total dose was given at the beginning of the interval.

Rescue Pain Medication

For calculation of the total rescue pain medication usage (morphine equivalent) by time point, if a subject is discontinued early (e.g., dies, withdraws consent, is withdrawn from the study, or is lost to follow-up) before the end of the time interval (e.g., 24 hours after study drug administration), his or her total rescue pain medication usage through the time interval will be a projected amount. For example, if a subject discontinues early at 6 hours after surgery, the projected amounts through 24 hours will be actual amount + average amount (actual amount/6 hours) multiplied by the number of hours remaining in the time interval (24-6).

Adverse Event or Concomitant Medications Dates or Times

For AEs or concomitant medications with missing or partially missing start/stop date/time, the following imputation rules will be applied:

For partial start date/time:

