7.3. Description of Demographics and Baseline Characteristics

Demographics and baseline characteristics will be summarized by treatment group and for all subjects, separately for Part 1 and Part 2 for the safety analysis set and efficacy analysis set. The variables to be included in the summary are age, gender, ethnicity, race, American Society of Anesthesiologists (ASA) physical status class, height (cm), and weight (kg).

Conversions between units for height and weight will use the following formulas:

Weight (kg) = weight (lb) / 2.2046226

Height (cm) = height (in) / 2.54.

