7.6.2.2 Secondary Efficacy Variables

The secondary efficacy variables for this study are:

- Total postsurgical opioid consumption through 72 hours.
- Time to first opioid rescue.

For total postsurgical opioid consumption, opioid medications will be converted to a morphine equivalent amount (see the table below). The converted amounts will be totaled for each subject and used in the analysis. When fentanyl is given transdermally the total amount, prior to conversion, will be calculated as the start date/time of administration until the end date/time of administration or end date/time of 72 hours after surgery, whichever is sooner, multiplied by the dose. Projected amounts, for subjects who discontinue early, will be calculated as described in [Section 7.1.3](#).

Medication	Unit	Route	Conversion (Multiplication) Factor
Oxycodone	mg	PO	0.5
Oxycontin	mg	PO	0.5
Morphine	mg	IV	1
Hydromorphone (Dilaudid)	mg	IV	6.7
Hydromorphone (Dilaudid)	mg	PO	1.3
Fentanyl	mcg	IV	0.1
Fentanyl	mcg	Transdermal	0.5
Hydrocodone	mg	PO	0.33

IV = intravenous; PO = oral.

If unplanned rescue medications are administered, then the conversion factor will be determined post-hoc prior to breaking the blind. If a combination opioid is administered then the opioid portion of the medication will be converted and included in the calculations. Opioids given postsurgically with an indication like ‘anesthesia maintenance’ will not be included in the calculation of total opioids.

Prior to analysis, the natural logarithm transformation will be applied to the total amount. When total amount of opioids used is 0, the result will be changed to the lesser of 1 or 0.5 of the smallest total amount observed in the study prior to being transformed with the natural logarithm. To test for significant differences between each liposome bupivacaine dose and placebo (Part 1) and between the one liposome bupivacaine dose and placebo (Part 2), an analysis of variance (ANOVA) with treatment as the main effect will be used. Based on the

model, the LS means, LS mean difference between the two treatment groups, 95% CI for the LS mean difference(s) between liposome bupivacaine and placebo, and p-value will be reported.

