For the analysis of time to first opioid rescue, time to first opioid rescue will be computed in hours as the date/time of the first opioid rescue minus the date/time of the end of surgery. If a subject is not administered an opioid, the time to first administration will be censored at 72 hours after surgery or at the time of last follow-up, whichever is earliest. Time of last follow-up will be defined as the later of (1) the last pain assessment, (2) the start time of the last rescue or concomitant medication, or (3) the start time of the last AE.

Time to first opioid rescue will be analyzed by the Kaplan-Meier method. The n (%) of subjects administered an opioid as well as the n (%) of censored observations will be presented for each treatment group. In addition, Kaplan-Meier estimates in terms of the median and its 95% CI, and the 25th and 75th percentiles will be presented for each treatment. Log-rank tests will be used to compare each dose of liposome bupivacaine (Part 1) and the one dose of liposome bupivacaine (Part 2) to placebo.

For Part 2, the efficacy measures will be analyzed using a hierarchical fixed-sequence stepwise testing procedure. To protect the Type 1 error rate, the testing will be performed in a sequentially rejective fashion. First, the total postsurgical opioid consumption through 72 hours will be tested. If the test of opioid consumption is significant at the two-sided 0.05 level then, and only then, the time to first opioid rescue will be tested. Each test will be declared positive at the two-sided 0.05 significance level.

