7.6.2.3 Tertiary Efficacy Variables

For Part 1, no statistical tests will be performed on any of the tertiary efficacy variables. Only descriptive statistics will be shown for each treatment.

For Part 2, the following describes the statistical analyses to be performed.

NRS-R, NRS-A, and AUC of Pain Intensity Scores

For the tertiary efficacy variables NRS-R, NRS-A, and the AUCs of the NRS-R and NRS-A pain intensity scores, the same analyses as those for the primary efficacy variable will be performed, except that the baseline NRS-A score will be used as the covariate for all variables using the NRS-A.

Proportion of Subjects Who are Pain Free

Pain free is defined as an NRS-R pain intensity score of 0 or 1. The number and percentage of subjects who are pain free will be summarized by treatment group for each time point. A chi-square test will be used to compare liposome bupivacaine to placebo.

Total Postsurgical Opioid Consumption Through 24, 36, 48, and 60 Hours

For the tertiary efficacy variables total opioid consumption through each of the time periods, the same analysis as that for the secondary efficacy variable of total opioid consumption through 72 hours will be performed.

Subjects Who Receive Rescue Medication

The category of ‘Subjects who receive no rescue medication’ is defined as subjects who report not taking any medication on the four Rescue Medication eCRFs.

The category of ‘Subjects who only receive the IV hydromorphone bolus’ is defined as subjects who report taking IV hydromorphone (or other opioid medications) on the First Rescue Medication eCRF and report not taking a medication on either of the Second Rescue Medication eCRFs or on the Third Rescue Medication eCRF.

The category of ‘Subjects who receive the IV hydromorphone bolus and a second opioid medication’ is defined as subjects who report taking IV hydromorphone (or other opioid medication) on the First Rescue Medication eCRF and who report taking a medication on either of the Second Rescue Medication eCRFs and report not taking a medication on the Third Rescue Medication eCRF.

The category of ‘Subjects who receive the IV hydromorphone bolus, a second opioid medication, and conventional bupivacaine HCl’ is defined as subjects who report taking IV hydromorphone (or other opioid medication) on the First Rescue Medication eCRF, who report taking a medication on either or both of the Second Rescue Medication eCRFs, and bupivacaine HCl on the Third Rescue Medication eCRF.

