CI = confidence interval; LB = liposome bupivacaine; LSM = least squares mean,
If the total amount of opioid used was 0 mg, the value was set to the lesser of 1 mg or one half of the smallest total amount observed in the study prior to being transformed into the natural logarithm.

[1] From an analysis of variance with treatment as the main effect on natural log transformed opioid amount.

Results are presented in the original, non-transformed scale.

[2] Geometric LSM ratio is the anti-log LSM difference (LB/placebo).

Reference: [Listing 16.5.2.1](#).

Pacira Pharmaceuticals, Inc.
402-C-323

Table 14.2.2.3-1 (Page x of Y)
Time to First Opioid Rescue
Study Part 1
(Efficacy Analysis Set)

	LB 67 mg (N=XX)	LB 133 mg (N=XX)	LB 266 mg (N=XX)	Placebo (N=XX)
Subjects Administered an Opioid Rescue [n (%)]	00 (00.00)	00 (00.00)	00 (00.00)	00 (00.00)
Censored Observations [n (%)]	00 (00.00)	00 (00.00)	00 (00.00)	00 (00.00)
Quartiles (hours) [1]				
First Quartile (25% Administered an Opioid)	000	000	000	000
Median (50% Administered an Opioid)	000	000	000	000
Third Quartile (75% Administered an Opioid)	000	000	000	000
Minimum, Maximum	00, 00*	00, 00*	00, 00*	00, 00*
95% CI of Median	(000, 000)	(000, 000)	(000, 000)	(000, 000)
P-value from Log-Rank Test	0.0000	0.0000	0.0000	0.0000

* indicates a censored observation.

CI = confidence interval; LB = liposome bupivacaine,

[1] Estimates from a Kaplan-Meier Analysis.

Reference: [Listing 16.5.2.1](#).

Pacira Pharmaceuticals, Inc.
402-C-323

Table 14.2.2.4-1 (Page x of Y)
NRS-R Pain Intensity Scores
Study Part 1
(Efficacy Analysis Set)

Time Point	Statistics	LB 67 mg (N=XX)	LB 133 mg (N=XX)	LB 266 mg (N=XX)	Placebo (N=XX)
Baseline	n	00	00	00	00
	Mean	00.0	00.0	00.0	00.0
	SD	00.00	00.00	00.00	00.00
	Median	00.0	00.0	00.0	00.0
	Minimum, Maximum	00, 00	00, 00	00, 00	00, 00
	95% CI about the Mean	00.0, 00.0	00.0, 00.0	00.0, 00.0	00.0, 00.0
First Request	n	00	00	00	00
	Mean	00.0	00.0	00.0	00.0
	SD	00.00	00.00	00.00	00.00
	Median	00.0	00.0	00.0	00.0
	Minimum, Maximum	00, 00	00, 00	00, 00	00, 00
	95% CI about the Mean	00.0, 00.0	00.0, 00.0	00.0, 00.0	00.0, 00.0
2 Hours	n	00	00	00	00
	Mean	00.0	00.0	00.0	00.0
	SD	00.00	00.00	00.00	00.00
	Median	00.0	00.0	00.0	00.0
	Minimum, Maximum	00, 00	00, 00	00, 00	00, 00
	95% CI about the Mean	00.0, 00.0	00.0, 00.0	00.0, 00.0	00.0, 00.0
Etc.					

CI = confidence interval; LB = liposome bupivacaine; NRS-R = numeric rating scale at rest.

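### Two SAP derivation rules fail as written: the substitute for a zero opioid total is itself 0, so its log is undefined, and inches are divided by 2.54 to give centimetres

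*SAP*

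**What the plan says.** **Zero totals.** SAP 7.6.2.2 converts opioids to morphine equivalents, sums them per subject and takes the natural log before an ANOVA. For a total of 0, "the result will be changed to the lesser of 1 or 0.5 of the smallest total amount observed in the study". The footnotes of Tables 14.2.2.2-1 (Part 1, 72 h), 14.2.2.2-2 (Part 2, 72 h) and 14.2.2.10-2 (Part 2, 24 to 60 h) repeat it: "the value was set to the lesser of 1 mg or one half of the smallest total amount observed in the study". Protocol 15.6.3.2 specifies the log transformation and has no rule for zeros.

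The plan expects zero totals. The tertiary endpoints include a category for subjects with no rescue medication, and for time to first rescue SAP 7.6.2.2 states: "If a subject is not administered an opioid, the time to first administration will be censored at 72 hours after surgery". For the totals through 24, 36, 48 and 60 h, SAP 7.6.2.3 says that "the same analysis as that for the secondary efficacy variable of total opioid consumption through 72 hours will be performed".

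**Height.** SAP 7.3 gives "Height (cm) = height (in) / 2.54".

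**The concern.** A rule that exists to make the log computable should return a positive number. This one returns 0 in every case in which it is used. The endpoint is the first secondary test in the Part 2 hierarchy (SAP 7.1.4), so its p-value decides whether time to first opioid rescue is tested at all. Four tertiary analyses inherit the rule. In those, a zero also arises for anyone whose first opioid comes after the cut-off. If the undefined log becomes a missing value, the subjects with the best possible outcome leave the analysis.

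The reference set for the minimum is open as well. Observed 'in the study' could cover both Parts, whereas the Protocol Synopsis says: "The efficacy results from Part 2 will not include data from Part 1". No time interval is named either.

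The height formula uses the wrong operator and would print impossible values for any height recorded in inches.

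**Working it through.** **1. The rule as written.** At least one total is 0, so the smallest observed total is 0.
- Reading A, the lesser of 1 and (0.5 × smallest): min(1, 0.5 × 0) = 0.
- Reading B, (the lesser of 1 and 0.5) × smallest: 0.5 × 0 = 0.

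Either way the value to be logged is 0, and ln(0) is undefined. As an illustration, totals of 0, 3.35, 20, 45 and 80 mg give a substitute of 0. Taking the smallest non-zero total instead gives min(1, 0.5 × 3.35) = min(1, 1.675) = 1 mg.

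**2. Early discontinuation does not repair it.** SAP 7.1.3 projects totals for subjects who stop early: "the projected amounts through 24 hours will be actual amount + average amount (actual amount/6 hours) multiplied by the number of hours remaining". For an opioid-free subject who stops at 6 h this is 0 + (0/6) × (24 − 6) = 0.

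**3. The intended substitute.** The planned first rescue is 0.5 mg IV hydromorphone (SAP 4) with a conversion factor of 6.7 (SAP 7.6.2.2): 0.5 × 6.7 = 3.35 mg. Half is 1.675, so the substitute is 1 mg. The half-minimum takes over only when the smallest non-zero total is below 2 mg. The SAP allows for departures from the planned first rescue ("report taking IV hydromorphone (or other opioid medication) on the First Rescue Medication eCRF"), but it gives no dose for them. If the smallest non-zero total were 1 mg (assumed), the substitute would be 0.5 mg.

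**4. Effect of keeping rather than losing one opioid-free subject.** Take an arm of n = 90 (SAP 8), an assumed geometric mean G among users, and substitute s. The arm's mean log falls by [ln(G) − ln(s)]/90, and its geometric mean falls by 1 − exp(−fall).

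| s | G (assumed) | Fall in mean log | Fall in geometric mean |
|---|---|---|---|
| 1 mg | 20 mg | ln(20)/90 = 0.033 | 3.3% |
| 1 mg | 100 mg | ln(100)/90 = 0.051 | 5.0% |
| 0.5 mg | 20 mg | ln(40)/90 = 0.041 | 4.0% |
| 0.5 mg | 100 mg | ln(200)/90 = 0.059 | 5.7% |

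Moving from a 1 mg to a 0.5 mg substitute changes the mean log by ln(2)/90 = 0.008 per zero subject. With G = 50 mg (assumed) and s = 1 mg, keeping k zeros multiplies the geometric mean by exp(−k × ln(50)/90): about 0.96 for k = 1, 0.81 for k = 5 and 0.68 for k = 9.

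**5. Height.** As written, 70/2.54 = 27.6 cm. Correctly, 70 × 2.54 = 177.8 cm. The error is a factor of 2.54² = 6.45. The weight formula beside it is right: 110/2.2046226 = 49.9 kg, which agrees with the 50 kg (110 pounds) in the protocol's exclusion criterion 7.

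**The case against.** The best reply is that the intent is obvious. A substitute made just before a log cannot be meant to be 0, so any competent programmer would use the smallest non-zero total. Harm needs two things that the documents do not show: at least one zero total, and code that follows the literal text and lets the undefined log become missing. Protocol 9.2 describes pain after this surgery as intense and lasting, so zero totals through 72 h may be few. The reference-set question has no effect under planned rescue, because the substitute is 1 mg in either Part and any interval. The 0.008 figure also depends on the assumed 1 mg minimum: a smallest total of 0.5 mg would give a substitute of 0.25 mg and a difference of ln(4)/90 = 0.015. The height error is conspicuous and enters no model.

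Most of this stands as a limit on size. It does not rescue the wording. A SAP rule for a gated endpoint should not depend on the programmer correcting it, and once 'non-zero' is assumed, the SAP still does not say which Part or interval supplies the minimum. It is also fair that fixing this before unblinding can apply only to Part 2, since the Part 1 data have already been reviewed unblinded to select the dose.

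**Conclusion.** Both rules are wrong as written, and nothing elsewhere in the documents corrects them.

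The zero-total rule should be fixed because it feeds the first gated secondary endpoint. Its effect is nil if no total is 0. Otherwise it is about 3% to 5% of an arm's geometric mean per opioid-free subject lost, given 90 per arm, a 1 mg substitute and an assumed geometric mean of 20 to 100 mg among users. The number of zero totals is unknown. The direction of any change in the p-value cannot be stated, because dropping such subjects alters the residual variance as well as the means. The choice of reference set matters only if some non-zero total is below 2 mg. The primary endpoint and its power statement are unaffected.

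The height error is confined to the height rows of the demographic tables and to Listing 16.8. Height is in no efficacy model, and BMI is not among the summarised variables.

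**What to change.** - In SAP 7.6.2.2 and the footnotes of Tables 14.2.2.2-1, 14.2.2.2-2 and 14.2.2.10-2, define the substitute as the lesser of 1 mg and half the smallest **non-zero** total observed. Keep the half-minimum, so that a zero never ties with or exceeds a real user whose total is below 2 mg.
- Add one sentence, before Part 2 is unblinded, saying whether the minimum is taken per Part and per time interval. A per-Part minimum would agree with the protocol's separation of Part 1 and Part 2 efficacy.
- In SAP 7.3, write height (cm) = height (in) × 2.54.
- As a minor clarification that adds no weight to this point, state that the transdermal fentanyl dose in SAP 7.6.2.2 is per hour and that its duration is limited to the period analysed. No error in the conversion factor is shown.

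The cost is one word in four places, one sentence, one operator and one clarifying phrase. No new data are needed.

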12. STUDY ENDPOINTS AND MEASUREMENTS

12.1. Efficacy Assessments

The following efficacy measurements will be conducted at the times specified after the end of surgery:

- Pain intensity scores using the NRS-R at baseline (prior to the nerve block) and 2, 4, 8, 12, 24, 36, 48, 60, and 72 hours, and at first request for rescue pain medication ([Appendix 1](#)).
- Pain intensity scores using the NRS-A (where the prescribed activity is actively flexing the involved knee up to 45 degrees) at baseline (prior to the nerve block) and 2, 4, 8, 12, 24, 36, 48, 60, and 72 hours, and at first request for rescue pain medication ([Appendix 1](#)).
- Time of first opioid rescue.
- Opioid use.
- Conventional bupivacaine HCl use.
- Sensory function assessment (i.e., cold test) at baseline, when the subject wakes up after surgery (general surgery subjects only), and at 2, 4, 12, 24, 36, 48, 60, and 72 hours after surgery, or until the subject's sensitivity to cold is demonstrated on two consecutive evaluations.
- Overall benefit of analgesia score questionnaire at 24, 48, and 72 hours ([Appendix 3](#)).
- Subject satisfaction with postsurgical pain control at 72 hours and Day 30 using a 5-point Likert scale ([Appendix 4](#)).
- Predefined treatment-emergent opioid-related AEs at 72 hours following surgery during Part 1 only ([Appendix 6](#)).

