13.3. Baseline Procedures (Day -1 to Day 1)

- Confirm eligibility.
- Update relevant medical/surgical history.
- Perform urine pregnancy test for women of childbearing potential before study drug administration.
- Perform urine drug screen.
- Perform physical examination.
- Measure vital signs (heart rate and blood pressure) after subject has rested for at least 5 minutes in the supine visit.
- Record subject's baseline assessment of pain intensity using the NRS-R followed by the NRS-A (see [Appendix 1](#)).
- Perform neurological assessment (see [Appendix 2](#)).
- Start 12-lead digital ECG recording approximately 1 hour prior to study drug administration.
- Perform sensory function assessment (cold test).
- Part 1 only: Collect baseline blood sample for PK analysis (specific sites only).
- Record concomitant medications taken within 3 days prior to surgery.
- Randomize subject and prepare study drug (Day 1).
- Administer study drug according to the randomization schedule within 2 hours prior to the surgical procedure.
- Record start and stop time of study drug administration.
- At the conclusion of the block, place and hep-lock the femoral nerve catheter.
- Record AEs starting after subject randomization.

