15.6.3.2 Secondary Efficacy Measures

The secondary efficacy measures for Part 2 of this study are:

- Total postsurgical opioid consumption through 72 hours
- Time to first opioid rescue.

These efficacy measures will be analyzed using a hierarchical fixed-sequence stepwise testing procedure. To protect the Type 1 error rate, the testing will be performed in a sequentially rejective fashion. First the total postsurgical opioid consumption through 72 hours will be tested. If the test of opioid consumption is significant at the two-sided 0.05 level then, and only then, the time to first opioid rescue will be tested. Each test will be declared positive at the two-sided 0.05 significance level.

For total postsurgical opioid consumption, opioid medications will be converted to a morphine equivalent amount. All opioids administered through 72 hours will be included in the analysis. Prior to analysis, the natural logarithm transformation will be applied to the total amount. To test for significant differences between liposome bupivacaine and placebo an analysis of variance (ANOVA) with treatment as the main effect will be used. Based on the model, liposome bupivacaine will be compared to placebo and a two-sided 95% CI about the differences will be presented.

The time from end of surgery to the first use of an opioid rescue through 72 hours after surgery will be summarized with medians and Kaplan-Meier estimates. A log-rank test will be used to compare liposome bupivacaine to placebo.

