15.6.3.3 Tertiary Efficacy Measures

Continuous Measures of Efficacy

For AUC of pain intensity scores, missing data will be imputed as described in [Section 15.5](#) and fully described in the SAP.

For total postsurgical opioid consumption, opioid medications will be converted to a morphine equivalent amount. All opioids administered through the specified time period will be included in the analysis. Prior to analysis, the natural logarithm transformation will be applied to the total amount.

Part 1

At the end of the study, summary statistics for each measure will be shown at each time point by treatment group. No statistical tests will be performed.

Part 2

Summary statistics for each measure will be shown at each time point by treatment group. To test for significant differences between liposome bupivacaine and placebo with respect to continuous measures of efficacy, an ANOVA with treatment as the main effect or ANCOVA with treatment as the main effect and the baseline value as the covariate will be used. Based on the model, liposome bupivacaine will be compared to placebo and two-sided 95% CIs about the differences will be presented.

Categorical Measures of Efficacy

Part 1

At the end of the study, the proportion of subjects in each category will be calculated and summarized at each time point by treatment group. No statistical tests will be performed.

Part 2

The proportion of subjects in each category will be calculated and summarized at each time point by treatment group. A chi-square test or Cochran-Mantel-Haenszel test will be used to compare liposome bupivacaine to placebo.

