7.1.4. Multiplicity Adjustments

Part 1

The purpose of Part 1 of the study is to select a dose for use in Part 2. Therefore, no alpha-level adjustments for multiple comparisons between the three doses and placebo will be made.

Part 2

Since no multiple comparisons of the primary efficacy variable will be made, no alpha-adjustments will be made.

Also, since there is only one primary efficacy variable and all other efficacy variables are considered secondary, no alpha-adjustments for the primary response variable will be made.

There are two secondary efficacy variables that will be analyzed using a hierarchical fixed-sequence stepwise testing procedure (See [Section 7.6.1](#)). The two secondary efficacy variables will only be analyzed if the primary efficacy variable is statistically significant at the two-sided 0.05 significance level. To protect the Type 1 error rate, the testing will be performed in a sequentially rejective fashion. First, the total postsurgical opioid consumption through 72 hours will be tested. If the test of opioid consumption is significant at the two-sided 0.05 level then, and only then, the time to first opioid rescue will be tested. Each test will be declared positive at the two-sided 0.05 significance level.

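### Part 2 opioid consumption, the test that opens time to first rescue, is analysed without baseline pain; adding baseline NRS-R costs almost nothing and gains precision if it predicts opioid use

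*SAP*

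**What the plan says.** SAP 7.6.2.2 converts opioids to morphine equivalents, totals them through 72 hours, takes the natural logarithm and then states that "an analysis of variance (ANOVA) with treatment as the main effect will be used". The protocol agrees. Section 15.6.3.2 reads "To test for significant differences between liposome bupivacaine and placebo an analysis of variance (ANOVA) with treatment as the main effect will be used", and the Part 2 paragraph of the synopsis has the comparison made "using ANOVA after a natural logarithm transformation for total postsurgical opioid consumption". SAP 7.6.2.3 carries the same model over to the 24, 36, 48 and 60 hour totals.

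The test sits inside a fixed sequence. SAP 7.1.4 says "The two secondary efficacy variables will only be analyzed if the primary efficacy variable is statistically significant at the two-sided 0.05 significance level". SAP 7.6.2.2 then adds "If the test of opioid consumption is significant at the two-sided 0.05 level then, and only then, the time to first opioid rescue" is tested.

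The primary endpoint is handled differently: SAP 7.6.2.1 uses ANCOVA with baseline NRS-R as the covariate. That score is taken before the nerve block (protocol 12.1), and protocol 13.3 lists the "baseline assessment of pain intensity using the NRS-R followed by the NRS-A" among the baseline procedures. For continuous tertiary measures, protocol 15.6.3.3 allows either a treatment-only ANOVA or "ANCOVA with treatment as the main effect and the baseline value as the covariate will be used".

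**The concern.** A pre-treatment variable that predicts the outcome can go into the model without bias, and it removes residual variance. Baseline NRS-R is such a candidate: it is measured before the block, it is already collected, and it already adjusts the primary endpoint. The documents give no reason for leaving it out of the opioid model. Opioid consumption has no baseline value of its own, but a covariate need not be the outcome's own baseline to be useful.

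This test matters more than most because it is the second step of the sequence. If it misses, opioid consumption is not claimed and time to first opioid rescue is not tested. SAP section 8 gives power for the primary endpoint only. No effect size, standard deviation or power is stated for opioid consumption, so its margin is unknown. If baseline pain does predict opioid use, the planned test has a wider interval and less power than the same data allow.

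**Working it through.** **The plan's own figure.** SAP section 8 and protocol 15.3 give a difference of 61, SD 104, 90 per arm, two-sided 0.05 and power above 97%. The noncentrality is 61 / (104 × √(2/90)) = 3.935. With 178 error degrees of freedom the power is 97.5% (97.6% by the normal approximation). The figure reproduces, but it concerns the primary endpoint only.

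**Inputs for the opioid test.** N = 180, 90 per arm (protocol 11.3.1; SAP section 8 records no increase after Part 1). Two-sided 0.05 (SAP 7.1). Two inputs are not in the documents and are assumed over a range:
- r, the within-arm correlation of baseline NRS-R with log consumption: 0 to 0.5.
- The power of the unadjusted ANOVA: 60% to 90%.

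**Precision.** Relative to ANOVA, the standard error of the adjusted difference is multiplied on average by

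f(r) = √[(1 − r²)(1 + 1/(N − 4))] = √[(1 − r²)(1 + 1/176)].

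The second factor allows for chance imbalance in the covariate. Error degrees of freedom fall from 178 to 177, which moves the critical t from 1.9734 to 1.9735. The interval-width ratio is f(r) × t(0.975, 177) / t(0.975, 178).

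**Power.** Choose the noncentrality that gives the assumed power at 178 degrees of freedom (2.817 for 80%), divide it by f(r), and read the power at 177 degrees of freedom.

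| r | f(r) | Change in CI width | from 60% | from 70% | from 80% | from 90% |
|---|---|---|---|---|---|---|
| 0 | 1.0028 | +0.29% | 59.8% | 69.8% | 79.8% | 89.8% |
| 0.1 | 0.9978 | −0.22% | 60.2% | 70.2% | 80.2% | 90.1% |
| 0.2 | 0.9826 | −1.74% | 61.5% | 71.5% | 81.4% | 91.0% |
| 0.3 | 0.9566 | −4.33% | 63.8% | 73.8% | 83.4% | 92.3% |
| 0.5 | 0.8685 | −13.15% | 72.2% | 81.6% | 89.7% | 96.2% |

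**Break-even.** Setting the width ratio to 1 gives |r| = 0.076. Power breaks even at the same value in all four columns.

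**In subjects.** The variance ratio at r = 0.3 is 0.91 × 1.0057 = 0.915, so the adjusted analysis of 180 subjects is worth about 180 / 0.915 = 197 unadjusted ones. At r = 0.5 the ratio is 0.754, or about 239.

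**Simulation.** With 40,000 trials per value of r at 80% unadjusted power, adjusted power came out at 80.0%, 80.1%, 81.4%, 83.2% and 89.9% for the five values of r (Monte Carlo error about 0.2 points). In a separate run of 10,000 trials per setting, type I error was 4.9% to 5.1% with and without the covariate.

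All these powers are for the opioid test alone, not conditional on the primary endpoint being significant.

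**The case against.** **There is no defect to correct.** The synopsis, protocol 15.6.3.2 and the SAP agree on a valid test. The plan also follows a recognisable convention: adjust for the outcome's own baseline where there is one, and otherwise use ANOVA. That stands, and it is why this is a suggested improvement.

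**The benefit rests on an unknown r.** This also stands. At 80% power the gain is 0.2 points at r = 0.1 and 1.4 at r = 0.2. The large figures need r = 0.5, for which the documents offer no support. Eligibility removes recent opioid users and people with other painful conditions, and PCA dose and lockout follow site practice; both could weaken the correlation. If the opioid test already had 97% power, the gain at r = 0.3 would be only about 1.0 point. What remains is the asymmetry: the loss at r = 0 is about 0.2 points.

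**Missing baselines.** The SAP has no explicit rule for a missing baseline NRS-R. The ANOVA does not need that score, whereas a complete-case ANCOVA drops anyone without it. If 2, 4 or 6 of 180 were missing (assumed counts), break-even |r| would rise to about 0.13, 0.17 or 0.20. With 4 missing and r = 0.1, 80% power would become 79.3%. The arithmetic is right, and it means the 0.2-point cost assumes complete baselines. But this is a required assessment before the block, the primary ANCOVA has the same gap, and a retained ANOVA still uses every subject.

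**Timing.** The SAP was revised after Part 1 had been reviewed, and the change would make the Part 2 model differ from Part 1. Part 1 efficacy data are analysed separately, so a change fixed before Part 2 is unblinded does not draw on Part 2 results.

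**Conclusion.** The point holds as a low-cost improvement, with medium confidence in its practical value. The treatment-only ANOVA is valid, and nothing in the plan is wrong or inconsistent here. Adding baseline NRS-R would change the power of the opioid test by about −0.2 points at r = 0, by +2.3 to +3.8 points at r = 0.3 and by +6.2 to +12.2 points at r = 0.5, for assumed unadjusted power between 90% and 60%. These figures assume 90 analysed per arm with complete baselines. Neither r nor the power of the opioid test is in the documents, and the true gain may be near zero. The case for acting is that the possible loss is very small, the covariate is already in hand, and the test controls access to the last secondary endpoint.

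**What to change.** Before Part 2 is unblinded:

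- Amend SAP 7.6.2.2, for Part 2 only, to analyse log opioid consumption by ANCOVA with treatment and baseline NRS-R, and keep the treatment-only ANOVA as a sensitivity analysis. The 24, 36, 48 and 60 hour totals follow through SAP 7.6.2.3.
- Update footnote [1] of Tables 14.2.2.2-2 and 14.2.2.10-2.
- Record the change from the protocol synopsis and from sections 15.6.3.2 and 15.6.3.3.
- Handle a missing baseline NRS-R in the same way as in the primary ANCOVA. Since the SAP states no rule for that, one sentence should cover both models.

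If Part 2 is already unblinded, leave the ANOVA as the planned test and report the ANCOVA as supportive only.

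The cost is SAP wording, two footnotes and a recorded protocol departure, with no new data. The statistical price is one degree of freedom, about 0.2 power points if r is near zero, and a model that differs from Part 1 for the same endpoint. Part 1 data could be used to estimate r beforehand.
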